### **6.4.1 Primary Efficacy Endpoint**

The primary efficacy endpoint is clinical remission at Week 12 (see definition of clinical remission in Section 2). A comparison between the vixarelimab arms and the placebo arm will be carried out. The difference between vixarelimab arms versus placebo arm in the proportion of patients with clinical remission at Week 12 will be evaluated by the Cochran-Mantel-Haenszel test, stratified by advanced or conventional failure and baseline mMS [REDACTED]. The non-responder imputation method, where subjects with missing data at scheduled assessment visits will be considered as “not achieved” for the clinical remission, will be used for primary analysis. A subgroup (advanced failure) analysis for the primary efficacy endpoint will be conducted *using the same methods outlined above, except that the Cochran-Mantel-Haenszel test will be stratified by baseline mMS [REDACTED]*.

### **6.4.2      Secondary Efficacy Endpoints**

The secondary efficacy endpoints are defined in Section 2. The secondary efficacy endpoints will be summarized by descriptive statistics based on the following calculations:

- Proportion of patients with clinical response at Week 12
- Proportion of patients with endoscopic improvement at Week 12
- Proportion of patients with endoscopic remission at Week 12

Data will be summarized by treatment arms. In addition, the secondary endpoints will be analyzed in the advanced failure subgroup.

### **6.4.3      Exploratory Efficacy Endpoints**

The exploratory efficacy endpoints are defined in Section 2. The exploratory efficacy endpoints will be summarized by descriptive statistics based on the following calculations:

- Proportion of patients with sustained remission at [REDACTED] Week 12 [REDACTED]
- Proportion of patients with clinical remission [REDACTED]
- Proportion of patients with clinical response [REDACTED]
- Proportion of patients with endoscopic improvement [REDACTED]
- Proportion of patients with endoscopic remission [REDACTED]
- Change from baseline in UC bowel movement signs and symptoms at Week 12 [REDACTED] as assessed by UC-PRO/SS score
- Improvement in UC bowel movement signs and symptoms at Week 12 [REDACTED] as defined by the proportion of patients with a  $\geq 6$ -point decrease in the UC-PRO/SS bowel domain score
- Change from baseline in UC functional signs and symptoms at Week 12 [REDACTED], as assessed by UC-PRO/SS score
- Improvement in UC functional symptoms at Week 12 [REDACTED], as defined by the proportion of patients with a  $\geq 2$ -point decrease in the UC-PRO/SS functional domain score

Data will be summarized by treatment arms.

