**Table 1 Objectives and Corresponding Endpoints (cont.)**

Exploratory Objectives	Corresponding Endpoints

 
To evaluate the long-term efficacy of vixarelimab
 
	
 
Sustained remission, defined as clinical remission at [REDACTED] Week 12 [REDACTED]
 
Clinical remission at [REDACTED]
 
Clinical response at [REDACTED]
 
Endoscopic improvement at [REDACTED]
 
Endoscopic remission at [REDACTED]
 
Change from baseline in UC bowel movement signs and symptoms at Week 12 and [REDACTED], as assessed by UC-PRO/SS score
 
Improvement in UC bowel movement signs and symptoms at Week 12 [REDACTED], as defined by the proportion of patients with a <math>\geq 6</math>-point decrease in the UC-PRO/SS bowel domain score
 
Change from baseline in UC functional signs and symptoms at Week 12 and [REDACTED], as assessed by UC-PRO/SS score
 
Improvement in UC functional symptoms at Week 12 and [REDACTED], as defined by the proportion of patients with a <math>\geq 2</math>-point decrease in the UC-PRO/SS functional domain score
 

 
To evaluate potential relationships between vixarelimab exposure and the efficacy and safety of vixarelimab
 
	
 
Relationship between PK parameters for vixarelimab and efficacy endpoints
 
Relationship between PK parameters for vixarelimab and safety endpoints
 

 
To evaluate potential relationships between selected covariates and exposure to vixarelimab
 
	
 
Relationship between selected covariates and PK parameters for vixarelimab
 

 
To evaluate potential effects of ADAs
 
	
 
Relationship between ADA status and efficacy, safety, or PK endpoints
 

ADA=anti-drug antibody; PK=pharmacokinetic; UC=ulcerative colitis; UC-PRO/SS=Ulcerative Colitis Patient-Reported Outcomes Signs and Symptoms.

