## **6.4 EFFICACY ANALYSES**

The analysis population for the efficacy analyses will be the modified intent-to-treat population defined as all patients who received at least one dose of study treatment and have at least one postbaseline efficacy measurement, with patients grouped according to their assigned treatment.

Because the study is hypothesis-generating in nature, hypothesis testing will be carried out in an exploratory fashion, at a two-sided 0.20 significance level. [REDACTED]

[REDACTED]. A separate DAP will contain more details on the statistical analyses.

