## Appendix 1: Schedule of Activities for Induction

---

[figure not shown]
- p All women of childbearing potential will have a serum pregnancy test performed at screening. Urine pregnancy tests will be performed at specified subsequent visits during treatment, at the treatment discontinuation visit, and at [REDACTED] after the final dose of study treatment. Urine pregnancy tests will be reviewed prior to each study drug administration for confirmation of a negative result. If a urine pregnancy test is positive, it must be confirmed by a serum pregnancy test.
- q All patients will undergo either a colonoscopy or a flexible sigmoidoscopy at specified timepoints. Patients without documentation of a colonoscopy within 2 years prior to screening must undergo a colonoscopy in lieu of a flexible sigmoidoscopy at screening. The screening endoscopy will be used as efficacy baseline and for inclusion. Video recordings should be taken of the entire endoscopic procedure (colonoscopy or flexible sigmoidoscopy), starting from insertion into the bowel. Biopsies should be performed upon withdrawal of the endoscope from the bowel. Technical instructions for video recording and biopsy collection will be provided in the endoscopy and/or laboratory manual.
- r Tissue collected at screening will be analyzed for CMV, *if required (see Section 4.1.2)*, as determined by histologic examination or immunohistochemistry per local standards, and will undergo histopathologic examination for patients without a prior histopathology report. Tissue collected at screening and subsequent timepoints will also be used for histologic assessments and exploratory biomarker research *at participating sites, excluding China (see Appendix 9)*. *For endoscopy assessments after screening for sites located in China, endoscopy will be performed but no biopsy will be collected.*
- s See [Appendix 3](#). *The Mayo Score will be calculated by the Sponsor.*
- t Clinician-reported outcome instruments will be completed after the physical examination, prior to the administration of study treatment.
- u An electronic diary will be used to collect PRO data, including stool frequency/rectal bleeding and the UC-PRO/SS instrument (see Section 4.5.7.2). Stool frequency and rectal bleeding will be recorded daily; UC-PRO/SS will be collected daily during screening and daily over at least a 7-day period before each specified study visit.

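### Week 12 UC-PRO/SS changes are summarised unadjusted by arm under a long-term objective; a baseline- and stratum-adjusted difference from placebo would be more precise at almost no cost

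*Combined protocol and SAP*

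**What the plan says.** Table 1 places "Change from baseline in UC bowel movement signs and symptoms at Week 12 and" a redacted later time, together with the functional-domain change and the two responder versions, under the exploratory objective "To evaluate the long-term efficacy of vixarelimab". These endpoints appear under no induction objective.

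Section 6.4.3 gives the method: "The exploratory efficacy endpoints will be summarized by descriptive statistics based on the following calculations". The list includes "Change from baseline in UC bowel movement signs and symptoms at Week 12" and ends with "Data will be summarized by treatment arms". It names no between-arm estimate, interval, model or covariate. By contrast, the primary test in Section 6.4.1 is stratified by prior failure type and baseline modified Mayo Score, the factors used in randomisation (Section 4.2.1).

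The baseline score will be available. Appendix 1 (footnote u) states that "UC-PRO/SS will be collected daily during screening and daily over at least a 7-day period before each specified study visit".

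The only missing-data rule in the visible text is in Section 6.4.1 and is worded for clinical remission: "The non-responder imputation method, where subjects with missing data at scheduled assessment visits" are counted as not in remission. The efficacy population (Section 6.4) is "all patients who received at least one dose of study treatment and have at least one postbaseline efficacy measurement", so a patient can belong to it without a Week 12 score. Section 6.4 calls the study hypothesis-generating, tests at a two-sided 0.20 level and leaves further detail to a separate DAP.

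**The concern.** Three things sit awkwardly together.

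- **Placement.** Placebo patients who enter the extension receive vixarelimab (Section 3.1.1), so only the induction period offers a randomised placebo contrast. The Week 12 symptom scores belong to that contrast but are filed with the long-term results.
- **Method.** Colleagues will compare the by-arm mean changes whether or not a comparison is planned. Unadjusted change wastes precision and carries part of any chance baseline imbalance into the difference. In a trial of about 210 patients, continuous symptom data are useful evidence of activity.
- **Early stoppers.** Use of prohibited therapy, including rescue for worsening disease, requires permanent discontinuation (Section 4.6.1). Patients who stop during induction have a discontinuation visit and then enter safety follow-up (Appendix 1, footnote c). Because the diary is tied to specified visits, many would probably lack a Week 12 score. A not-achieved category has no counterpart on a change scale, so the remission rule cannot simply be carried across.

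**Working it through.** The visible documents contain no SD, correlation, effect size or dropout rate for UC-PRO/SS, so there is no stated figure to reproduce. What follows is a range under assumptions.

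**Inputs.** About 210 patients and three arms (Sections 6.1 and 4.2.1). The allocation ratio is redacted; I assume 1:1:1, so 210/3 = 70 per arm. Two-sided 0.20 (Section 6.4) corresponds to an 80% CI with multiplier 1.2816. I assume r from 0.2 to 0.8 and equal variances at baseline and Week 12.

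**Precision.** With n per arm and common variance σ²:

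- difference in unadjusted change: (2σ²/n) × 2(1 − r)
- ANCOVA difference adjusted for baseline: (2σ²/n) × (1 − r²)
- ratio: 2(1 − r)/[(1 − r)(1 + r)] = 2/(1 + r), above 1 for every r below 1

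The last column, 70 × (1 + r)/2, is the number per arm at which ANCOVA matches unadjusted change on 70 per arm.

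| r | Variance ratio | SE ratio | ANCOVA n per arm matching 70 |
|---|---|---|---|
| 0.2 | 1.67 | 1.29 | 42 |
| 0.3 | 1.54 | 1.24 | 45.5 |
| 0.5 | 1.33 | 1.15 | 52.5 |
| 0.7 | 1.18 | 1.08 | 59.5 |
| 0.8 | 1.11 | 1.05 | 63 |

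The 80% half-width in SD units is:

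- at r = 0.3, 1.2816 × √(1.4 × 2/70) = 0.26 unadjusted against 1.2816 × √(0.91 × 2/70) = 0.21 adjusted
- at r = 0.5, 1.2816 × √(1.0 × 2/70) = 0.22 against 1.2816 × √(0.75 × 2/70) = 0.19

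I stay in SD units because one SD in points would not suit both domains. The functional domain has three items; if each is scored 0 to 4 and they are summed, the range is 0 to 12.

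For an assumed true effect of 0.3 SD, power at the two-sided 0.20 level would be 0.59 unadjusted against 0.72 adjusted (r = 0.3), 0.69 against 0.78 (r = 0.5) and 0.84 against 0.89 (r = 0.7). These figures only illustrate the gain, since no such test is planned.

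**Early stoppers.** Assume a mean change among completers of −6 on vixarelimab and −4 on placebo, a difference of −2.0, and no change in those who stop. The all-patient difference is (1 − d_v)(−6) − (1 − d_p)(−4), where d_v and d_p are the dropout proportions on vixarelimab and placebo.

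| Dropout, vixarelimab / placebo | Calculation | All-patient difference |
|---|---|---|
| 5% / 10% | −5.70 + 3.60 | −2.10 |
| 5% / 15% | −5.70 + 3.40 | −2.30 |
| 8% / 20% | −5.52 + 3.20 | −2.32 |
| 10% / 10% | −5.40 + 3.60 | −1.80 |

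In the first three rows a completers-only table understates the drug effect; in the last it overstates it.

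**The case against.** The strongest reply is that this is a low-tier exploratory diary score in a hypothesis-generating trial. Even the secondary endpoints are only summarised descriptively (Section 6.4.2). No UC-PRO/SS comparison with placebo is planned, so no planned inference loses power. Detailed methods are deferred to a DAP that is not among these documents, and part of Section 6.4 is redacted, so adjustment or missing-data rules may already exist. All of that stands. It makes the point minor but does not remove the gain over the one method the text states.

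Several stronger readings are tempting and should not be drawn:

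- *The plan analyses observed cases and drops early failures.* The text says neither. Exclusion is a plausible default given the discontinuation pathway, but the handling is unspecified.
- *Every binary endpoint would count those patients as failures.* Non-responder imputation is stated for clinical remission only. The other binary endpoints, including the UC-PRO/SS responder endpoints (decreases of at least 6 and 2 points), have no stated rule in the visible text.
- *The omission flatters placebo.* That follows only under some dropout patterns; equal dropout reverses it above.
- *A repeated-measures model is plainly the answer.* The induction visit grid is not visible. If Week 12 is the only post-baseline UC-PRO/SS visit in induction, such a model reduces to ANCOVA on available cases. In any case it assumes data missing at random and does not itself treat early stoppers unfavourably.

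**Conclusion.** The concern holds as a minor, nearly free improvement. Two parts follow directly from the text: the Week 12 UC-PRO/SS endpoints sit under the wrong objective for a placebo-controlled timepoint, and the stated summary uses neither the baseline score nor the strata. The variance penalty, 2/(1 + r), exceeds 1 for any r below 1 under equal variances. Its size, 11% to 67%, rests entirely on assumed r of 0.8 to 0.2, and the per-arm figures also rest on assumed equal allocation. The gap on early stoppers and rescue users is real, but neither the size nor the direction of its effect can be determined from the documents. The primary analysis is not affected. If the DAP already specifies an adjusted estimate and a handling rule, only the Table 1 placement remains to be corrected.

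**What to change.** - In Table 1, list the Week 12 UC-PRO/SS endpoints under an induction-versus-placebo objective, keeping them exploratory. Leave the later timepoints under the long-term objective.
- In Section 6.4.3 or the DAP, for each domain, report the Week 12 difference for each vixarelimab arm versus placebo with an 80% CI, from an ANCOVA on baseline score and the two randomisation strata. If UC-PRO/SS is collected at several induction visits, a mixed model for repeated measures with the same covariates may be used instead.
- State how patients who discontinue or use rescue before Week 12 enter the main analysis and the responder endpoints. Add a sensitivity analysis that gives them an unfavourable value on the change scale, such as no change from baseline.
- Keep the descriptive tables by arm.

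The cost is a few lines of text and one standard model, settled before unblinding. The ANCOVA needs no new data, because the baseline score and strata are already collected. If the DAP already covers the analysis items, a cross-reference is enough.

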## **6.5      SAFETY ANALYSES**

The safety analysis population will consist of all randomized patients who received at least one dose of study treatment, with patients grouped according to treatment received.

Safety will be assessed by adverse events, clinical laboratory evaluations, vital signs, and ECGs.

Separate summaries of adverse events will be provided for the screening period, the induction period, and optional ATE period. Adverse events will be summarized by treatment arms.

All verbatim adverse event terms will be mapped to Medical Dictionary for Regulatory Activities thesaurus terms, and adverse event severity will be graded according to DAIDS toxicity grading scale.

Relevant laboratory, vital sign (e.g., pulse rate), and ECG data will be displayed by time, with grades identified where appropriate.

## **6.6 PHARMACOKINETIC ANALYSES**

The PK analysis population will consist of patients with at least one postdose serum PK sample in which vixarelimab concentration is evaluable, unless major protocol deviations or unavailability of information (e.g., exact blood sampling time) occurred which may interfere with PK evaluation, with patients grouped according to treatment arm.

Serum vixarelimab concentration data will be tabulated and summarized (mean, standard deviation, coefficient of variation, median, minimum, and maximum) at relevant timepoints. Inter-participant variability and drug accumulation will be evaluated.

Exploratory analyses may be conducted to evaluate potential relationships between drug exposure and efficacy/safety endpoints and to evaluate potential relationships between selected covariates and exposure to vixarelimab. Additional exploratory PK analyses (e.g., using PK data from this study in a population PK analysis) may be conducted as appropriate, and the results may be reported separately from this study report.

## **6.7 IMMUNOGENICITY ANALYSES**

The immunogenicity analysis population will consist of all patients with at least one postdose ADA assessment. Patients will be grouped according to treatment received or, if no treatment is received prior to study discontinuation, according to treatment assigned.

The numbers and proportions of ADA-positive patients and ADA-negative patients at baseline (baseline prevalence) and after drug administration (postbaseline incidence) will be summarized by treatment group. When determining postbaseline incidence, patients are considered to be ADA positive if they are ADA negative or have missing data at baseline but develop an ADA response following study drug exposure (treatment-induced ADA response), or if they are ADA positive at baseline and the titer of one or more postbaseline samples is at least 0.60 titer unit greater than the titer of the baseline sample (treatment-enhanced ADA response). Patients are considered to be ADA negative if they are ADA negative or have missing data at baseline and all postbaseline samples are negative, or if they are ADA positive at baseline but do not

[figure not shown]
have any postbaseline samples with a titer that is at least 0.60 titer unit greater than the titer of the baseline sample (treatment unaffected).

The relationship between ADA status and safety, efficacy, PK, and biomarker endpoints may be analyzed and reported via descriptive statistics.

## **6.8 BIOMARKER ANALYSES**

The PD biomarker analyses will include all patients with one pretreatment and at least one post-treatment biomarker assessment, with patients grouped according to the treatment received. PD biomarker analyses will include examination of changes from baseline (pretreatment) with post-treatment timepoints. PD biomarkers will be assessed as an absolute increase over time, and/or as a percent change relative to original baseline for each patient. In addition, efforts will be made to perform PK/PD analyses based on PD and PK exposure data. Results will be summarized through use of summary statistics and or other graphs as required. Descriptive statistics will be listed by dose, treatment arm, and response status. Additional PD analyses will be conducted as appropriate.

Additional (e.g., predictive, prognostic, pathway) biomarker analyses will include all patients with one pretreatment biomarker assessment, with patients grouped according to the treatment received, provided there are sufficient data in each biomarker arm to facilitate a meaningful analysis. Baseline values may be used to evaluate predictive biomarkers in the context of activity (clinical and/or pharmacological), drug levels, safety, and/or immunogenicity endpoints. Results will be summarized descriptively.

## **7. DATA COLLECTION AND MANAGEMENT**

### **7.1 DATA QUALITY ASSURANCE**

The Sponsor will be responsible for data management of this study, including quality checking of the data. Data entered manually will be collected via EDC through use of eCRFs. Sites will be responsible for data entry into the EDC system. In the event of discrepant data, the Sponsor will request data clarification from the sites, which the sites will resolve electronically in the EDC system.

The Sponsor will produce an EDC Study Specification document that describes the quality checking to be performed on the data. Central laboratory data, endoscopy scores, electronic diary data, and some ClinRO and PRO data will be sent directly to the Sponsor, using the Sponsor's standard procedures to handle and process the electronic transfer of these data.

eCRFs and correction documentation will be maintained in the EDC system's audit trail. System backups for data stored by the Sponsor and records retention for the study data will be consistent with the Sponsor's standard procedures.

PRO and ClinRO data will be collected through the use of an electronic device/portal provided by a vendor (see Section 7.3 for details).

ClinRO data may be collected on paper questionnaires. The data from the questionnaires will be entered into the EDC system by site staff.

## **7.2 ELECTRONIC CASE REPORT FORMS**

eCRFs are to be completed through use of a Sponsor-designated EDC system. Sites will receive training and have access to a manual for appropriate eCRF completion. eCRFs will be submitted electronically to the Sponsor and should be handled in accordance with instructions from the Sponsor.

All eCRFs should be completed by designated, trained site staff. eCRFs should be reviewed and electronically signed and dated by the investigator or a designee.

At the end of the study, the investigator will receive patient data for his or her site in a readable format that must be kept with the study records. Acknowledgement of receipt of the data is required.

## **7.3 ELECTRONIC PATIENT- AND CLINICIAN-REPORTED OUTCOME DATA**

An electronic device/portal will be used to capture PRO and ClinRO data. The device/portal is designed for entry of data in a way that is attributable, secure, and accurate, in compliance with FDA regulations for electronic records (21 CFR Part 11). The data will be transmitted to a centralized database maintained by the electronic device vendor.

The electronic data will be available for view access only, via a secure method. Only identified and trained users may view the data, and their actions will become part of the audit trail. The Sponsor will have view access only. System backups for data stored by the Sponsor and records retention for the study data will be consistent with the Sponsor's standard procedures.

Once the study is complete, the data, audit trail, and trial and system documentation will be archived. The investigator will receive patient data for the site in both human- and machine-readable formats that must be kept with the study records as source data. Acknowledgement of receipt of the data is required. In addition, the Sponsor will receive all data in a machine-readable format.

